### **16.4. VITAL SIGNS**

Vital sign data is collected at Visit 1 (Screening), Visit 2 (Day -2), Visit 2 (Day -1), Visit 2 (Day 1 – predose), Visit 2 (Week 2), Visit 3 (follow-up) and ET (Early termination). Weight is collected at Visit 1 (Screening), Visit 2 (Day -2), Visit 2 (Day 1 – predose), Visit 2 (Week 2), Visit 3 (follow-up) and ET (Early Termination). Height and BMI are collected at Visit 1 (Screening) only. Baseline height will be reported with demographics.

The following Vital Signs measurements will be reported for this study:

- Standing/ Supine Systolic Blood Pressure (mmHg)
- Standing/ Supine Diastolic Blood Pressure (mmHg)
- Standing/ Supine Pulse Rate (bpm)
- Respiratory Rate (breaths/min)
- Oral Body Temperature (C)
- Weight (kg)
- BMI (kg/m^2)

These vital signs will be summarized using descriptive statistics at each time point for SEP-363856 (Overall). Changes from baseline will be summarized in the same manner. The number and percentage of subjects with Sponsor defined PCS vital sign values (defined in the Section 16.4.1) will be presented for SEP-363856 (Overall) at each visit and for the overall post baseline period. For the individual visits, percentages will be calculated based on the number of safety population subjects with data available for the given parameter and time point. For the overall post-baseline period, percentages will be calculated based on the number of safety population subjects who had at least one non-missing post treatment test result for a particular parameter. Any early termination visit, follow-up visit or unscheduled visit that occurs after first dose will be included in the period of evaluation for PCS post-baseline.

The following summaries and listings will be provided for vital signs data:

- Actual value and change from baseline presented at each time point for SEP-363856 (Overall)
- Incidence of PCS values presented for SEP-363856 (Overall)
- Listing of vital signs data for all enrolled subjects.
- Listing of vital signs data meeting PCS criteria for all enrolled subjects

Document:	\\quintiles.net\enterprise\Apps\sasdata\SASa\sas\Sunovion\SEP- 363856\BZA44200\Biostatistics\Documentation\SAP\V1\SEP361-301 SAP Final V1.0_26JUL2023				
Author:		Version Number:	Final 1.0		
		Version Date:	26JUL2023		
Template No.	Femplate No.: CS TP BS016 Revision 5 Reference: CS WI BS005				

Effective Date: 01Apr2018

• The number and percentage of subjects with orthostatic hypotension and orthostatic tachycardia will be summarized for SEP-363856 (Overall), by time point and for the overall post-baseline period. Orthostatic hypotension and orthostatic tachycardia are defined in Section 16.4.2.

#### 16.4.1. VITAL SIGNS POTENTIALLY CLINICALLY SIGNIFICANT (PCS) CRITERIA

Potentially clinically significant vital signs measurements will be identified in accordance with the following predefined PCS criteria:

Parameter Name	PCS Low	PCS High
Standing/ Supine Systolic Blood Pressure (mmHg)	Value $\leq 90$ and $\geq 20$ decrease from baseline	Value $\ge 180$ and $\ge 20$ increase from baseline
Standing/ Supine Diastolic Blood Pressure (mmHg)	Value $\leq 50$ and $\geq 15$ decrease from baseline	Value $\geq 105$ and $\geq 15$ increase from baseline
Standing/ Supine Pulse Rate (beats/min)	Value $\leq 50$ and $\geq 15$ decrease from baseline	Value $\geq 120$ and $\geq 15$ increase from baseline
Weight (kg)	$\geq$ 7% decrease from baseline	$\geq$ 7% increase from baseline
Temperature (°C)	NA	Value $\ge$ 38.3°C and $\ge$ 0.8°C increase from baseline

.

### **16.5.** Physical and Neurological Examinations

Findings from the physical examination will be presented as follows:

Pre-existing clinically significant conditions recorded as medical history (at screening). Refer to Section 11 for data display of medical history.

New clinically significant conditions recorded as AEs (post baseline). Refer to Section 16.1 for data display of AEs.

### 16.6. COLUMBIA SUICIDE SEVERITY RATING SCALE (C-SSRS)

The C-SSRS is a tool designed to systematically assess and track suicidal behavior and suicidal ideation for lifetime, one month prior to the screening visit, and throughout the study. The strength of this suicide classification system is in its ability to comprehensively identify suicidal events while limiting the over-identification of suicidal behavior. The C-SSRS Baseline/Screening Version is used at the screening visit and the C-SSRS Since Last Visit Version is used from Visit 2 onward. Subjects with Type 4 (active suicidal ideation with some intent to act, without specific plan) or Type 5 (active suicidal ideation with specific plan and intent) suicidal ideation during the study will be discontinued from the study and referred to a mental health professional.

C-SSRS includes four sections: Suicidal Ideation, Intensity of Ideation, Suicidal Behavior, and Answer for Actual Suicide Attempts.

#### **C-SSRS** Categories

The following outcomes are C-SSRS categories and have binary responses (yes/no). The categories have been reordered from the actual scale to facilitate the definitions of the C-SSRS endpoints, and to provide clarity in the presentation of the results.

- Category 1 Wish to be Dead
- Category 2 Non-specific Active Suicidal Thoughts
- Category 3 Active Suicidal Ideation with Any Methods (Not Plan) without Intent to Act
- Category 4 Active Suicidal Ideation with Some Intent to Act, without Specific Plan
- Category 5 Active Suicidal Ideation with Specific Plan and Intent
- Category 6 Preparatory Acts or Behavior
- Category 7 Aborted Attempt
- Category 8 Interrupted Attempt
- Category 9 Actual Attempt (non-fatal)
- Category 10 Completed Suicide

The categories of the C-SSRS are not mutually exclusive. Subjects will be counted in each category for which they have an event.

Self-injurious behavior without suicidal intent is a non-suicide-related C-SSRS outcome, and also has a binary response (yes/no).

Document:	t: \\quintiles.net\enterprise\Apps\sasdata\SASa\sas\Sunovion\SEP- 363856\BZA44200\Biostatistics\Documentation\SAP\V1\SEP361-301 SAP Final V1.0_26JUL2023					
Author:		Version Number:	Final 1.0			
		Version Date:	26JUL2023			
Template No.:	CS TP BS016 Revision 5	Reference: 0	CS WI BS005			

Effective Date: 01Apr2018

Sumitomo Pharma PROTOCOL SEP361-118

#### Statistical Analysis Plan

Page 35 of 58

#### **C-SSRS** Analyses

For the purpose of C-SSRS analysis, "baseline" and "post-baseline" are defined as follows.

Time point	Study Visit	C-SSRS Version	Derivation Rule	
Baseline	Screening	Baseline/Screening - Past 1 Month	Most severe outcome	
Dusenne	Day -1	Since Last Visit		
Post-baseline	All post-baseline visits up to and including Week 3/Follow- up/End of Study, including unscheduled visits	Since Last Visit	Most severe outcome	

C-SSRS composite endpoints will be derived for each time point of interest (i.e. baseline, post baseline, and each study visit) as follows:

- Any suicidal ideation: A "yes" answer to any one of the 5 suicidal ideation questions on C-SSRS (Categories 1-5).
- Any suicidal behavior: A "yes" answer to any one of the 5 suicidal behavior questions on the C-SSRS (Categories 6-10).
- Any suicidality: A "yes" answer to any one of the 10 suicidal ideation and/or behavior questions on the C-SSRS (Categories 1-10).

For each subject, the suicidal ideation score at each time point of interest (i.e. baseline, post baseline, each study visit) is defined as the maximum suicidal ideation category (1-5) present for the time of interest. If no ideation is present a score of 0 is assigned. A suicidal ideation score of 4 or 5 is considered serious.

The number and percentage of subjects with any suicidality, any suicidal ideation and subtypes of ideation, any suicidal behavior and subtypes of behavior, and any non-suicidal self-injurious behavior will be presented for:

- Baseline (as defined above)
- Post-baseline (as defined above)
- Each scheduled study visit: Screening (Lifetime; Past 1 Month), Day -1, Week 2, Week 3 (Follow-up)

Shift in suicidal ideation score from baseline to the post-baseline time point and to each of the following study visits will be presented: Week 2, Week 3 (Follow-up)

Intensity of ideation for the most severe ideation subtype is measured in terms of frequency, duration, controllability, deterrents, and reasons for ideation. Each is measured with responses ranging from 1 to 5 for frequency and duration, and from 0 to 5 for controllability, deterrents, and reasons for ideation. The ideation intensity total score is the sum of responses to the five items and can range from 2 to 25 for subjects with endorsed suicidal ideation. For subjects with endorsed suicidal ideation, if one or more of these five items are missing at an assessment, the total score will be set to missing. If a subject did not endorse any suicidal ideation, a score of 0 for the ideation intensity total score will be given.

Actual lethality associated with actual attempts is rated on a 6-point scale from 0 = 'No physical damage or very minor physical damage' to 5 = 'Death'. Potential lethality of actual attempts (if actual lethality = 0) is rated on a 3-

Document:	\\quintiles.net\enterprise\Apps\sasdata\SASa\sas\Sunovion\S 363856\BZA44200\Biostatistics\Documentation\SAP\V1\SEF	SEP- 2 361-301 SAP Final \	/1.0_26JUL2023
Author:		Version Number:	Final 1.0
		Version Date:	26JUL2023
Template No.:	CS_TP_BS016 Revision 5	Reference: C	CS_WI_BS005

Effective Date: 01Apr2018

point scale from 0 = 'Behavior not likely to result in injury' to 2 = 'Behavior likely to result in death despite available medical care.

All C-SSRS responses will be listed for all subjects enrolled. The ideation intensity total score and the actual lethality and potential lethality of actual attempts will only be presented in data listings.

### **16.7. MOVEMENT DISORDER MEASURES**

Movement disorder measures include AIMS, BARS, and SAS. The BARS, AIMS, and SAS will be summarized descriptively by presenting summary statistics of actual values and change from baseline values. All data from the three scales will be presented in the data listings for all subjects enrolled.

#### Abnormal Involuntary Movement Scale (AIMS)

The AIMS is a clinician-rated assessment of abnormal movements consisting of unobtrusive observation of the subject at rest (with shoes removed) and several questions or instructions directed toward the subject. Using a severity scale ranging from 0 (none) to 4 (severe), clinicians rate dyskinesia in several body regions, including the facial area, extremities, and trunk. There are two items related to dental status, as well as three global impression items assessing overall severity, incapacitation, and the subject's awareness of abnormal movements (Guy-1976; Munetz-1988). AIMS total score will be calculated as the sum of items 1 through 7 (ranging from 0 to 28). If any item score contributing to the calculation of AIMS total score is missing, the total score will be set to missing. Items 8 through 12 will not be used in total score calculation. The global severity score (item 8) will be summarized separately.

AIMS total score (observed value and change from baseline) will be summarized numerically by visit. In addition, the AIMS total score at each visit will be classified as "abnormal" if: either at least two items (out of items 1 - 7) have a response of "mild" or higher, or at least one item (out of items 1 - 7) has a response of "moderate" or higher. Otherwise, the non-missing total score will be classified as "normal". This is a modification of the Schooler-Kane criteria for tardive dyskinesia. Shifts from baseline in AIMS total score classification will be summarized by visit and for the overall post-baseline period. Any early termination visit, follow-up visit or unscheduled visit that occurs after first dose will be included in the overall post-baseline period.

The AIMS global severity score will be summarized both numerically and categorically by visit.

The post-baseline AIMS global severity assessment will be classified as "worsened" (score is higher than baseline), "unchanged" (score is equal to baseline), or "improved" (score is lower than baseline), relative to a subject's baseline response. These post-baseline changes will be summarized by visit.

#### Barnes Akathisia Rating Scale (BARS)

The BARS is a rating scale geared toward assessment of neuroleptic-induced akathisia, though it can be used to measure akathisia associated with other drugs as well. The BARS consists of four items, including one item assessing objective restlessness, two items targeting subjective restlessness (awareness and related distress), and one global clinical assessment item. All items are anchored and utilize a 4-point scale, except for the global rating which has a 6-point scale (from absence of akathisia through severe akathisia). The subjective and objective items are summed to yield a total score (ranging from 0 to 9). If any item score contributing to the calculation of BARS total

Document:	\\quintiles.net\enterprise\Apps\sasdata\SASa\sas\Sunovion\SEP- 363856\BZA44200\Biostatistics\Documentation\SAP\V1\SEP361-301 SAP Final V1.0_26JUL2023		
Author:		Version Number:	Final 1.0
		Version Date:	26JUL2023
Template No.:	CS_TP_BS016 Revision 5	Reference: C	CS_WI_BS005

Effective Date: 01Apr2018

Page 37 of 58

score is missing, the total score will be set to missing.

BARS total score (observed value and change from baseline) will be summarized numerically by visit. In addition, the BARS item scores for the four items will be summarized both numerically and categorically by visit.

The post-baseline BARS global clinical assessment of akathisia will be classified as "worsened" (score is higher than baseline), "unchanged" (score is equal to baseline), or "improved" (score is lower than baseline), relative to a subject's baseline response. These post-baseline changes will be summarized by visit.

Simpson-Angus Scale (SAS)

The SAS is a clinician-rated assessment of neuroleptic-induced Parkinsonism consisting of 10 items. Items are anchor-based, rated on a 5-point scale of severity, and address rigidity, gait (bradykinesia), tremor, akathisia, shoulder shaking, glabellar tap, and salivation (Siddiqui-2009; Simpson-1970). SAS mean score is calculated as the average of all 10 item scores. If any item score is missing, the mean score will be set to missing.

SAS mean score (observed value and change from baseline) will be summarized numerically by visit. In addition, SAS mean score at each visit will be classified as "abnormal" if it exceeds 0.3. Otherwise, non-missing mean scores will be classified as "normal". Shifts from baseline in SAS mean score classification will be summarized by visit and for the overall post-baseline period. Any early termination visit, follow-up visit or unscheduled visit that occurs after first dose will be included in the overall post-baseline period.

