q Unscheduled BARS, AIMS, and SAS scales should be administered if a subject develops extrapyramidal symptoms (EPS) requiring treatment.

r All adverse events occurring after signing informed consent through the end of study will be collected.

s PANSS, BNSS, MADRS, CGI-S, and C-SSRS to be completed on Day -2 or Day -1.

t BARS, AMES, SAS to be collected on Day -1 or Day 1 (predose).

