### 5.2. Safety Objectives

- To evaluate the safety and tolerability of adjunctive administration with SEP-363856 (50 or 75 mg/day) in adults with schizophrenia.
- To assess whether adjunctive administration of SEP-363856 is associated with extrapyramidal symptoms as measured by the Barnes Akathisia Rating Scale (BARS), the Abnormal Involuntary Movement Scale (AIMS), and the Simpson-Angus Scale (SAS).

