### 6.2. Safety Endpoints

- Incidence of treatment emergent adverse events (TEAEs), serious AEs (SAEs) and AEs (or SAEs) leading to discontinuation.
- Absolute values and changes from baseline in clinical laboratory tests (hematology, serum chemistry, urinalysis), and clinical evaluations (vital signs, body weight, body mass index [BMI], 12-lead electrocardiogram [ECG] parameters).
- Frequency and severity of suicidal ideation or suicidal behavior as measured by the C-SSRS.
- Change from Baseline in BARS, AIMS and SAS scores at Week 2 and Week 3.

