#### Concomitant Psychotropic Medications:

Treatment with benztrapine up to 6 mg/day will be permitted, as needed, for movement disorders. In cases where benztrapine is not available or a subject has had an inadequate response or intolerance to benztrapine treatment, the following medications may be used to treat acute extrapyramidal symptoms (EPS): biperiden (up to 16 mg/day) or trihexyphenidyl (up to 15 mg/day) or diphenhydramine (up to 100 mg/day) or procyclidine (up to 30 mg/day). Treatment with propranolol (up to 120 mg/day) will be permitted as needed for akathisia.

Concomitant use of lorazepam, temazepam, eszopiclone, zaleplon, zolpidem, and zolpidem CR is permitted at the discretion of the Investigator with the following restrictions:

1. lorazepam (or equivalent benzodiazepine) is permitted for clinically significant anxiety/agitation or as a sedative/hypnotic up to a maximum daily dose of 6 mg/day. Intramuscular lorazepam is permitted up to 4 mg/day for acute anxiety/agitation, as clinically indicated. Lorazepam should be used sparingly, when clinically required, per Investigator judgment.

2. temazepam ( $\leq$  30 mg/day), eszopiclone ( $\leq$  3 mg/day), zaleplon ( $\leq$  20 mg/day), zolpidem ( $\leq$  10 mg/day), and zolpidem CR ( $\leq$  12.5 mg/day) may be administered at bedtime for insomnia, as needed.
3. hypnotic agents should be administered no more than once nightly and should not be used in combination.

The date and time of the last dose taken prior to scheduled efficacy assessments must be recorded at each visit. Subjects should be encouraged to avoid taking sedative/hypnotic medications within 8 hours of scheduled efficacy assessments.

Medications used for the treatment of anxiety/agitation and insomnia (eg, lorazepam and zolpidem) should not be used in close temporal proximity (defined as administration within 2 hours of each other).

Similar drugs at equivalent dosages will be permitted as described in the Operations Manual or in consultation with the Medical Monitor.

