# 7.3. RETESTS, UNSCHEDULED VISITS AND EARLY TERMINATION DATA

In general, for by-visit summaries, data recorded at the nominal visit will be presented.

In the case of a retest, the assessment recorded under the planned visit will be used for by-visit summaries, and the assessment(s) recorded under unscheduled visit(s) will be presented in listings only.

Early termination data will be mapped to the next scheduled or planned timepoint where an assessment is expected to be performed as specified by the Schedule of Assessment table in the Protocol for by-visit summaries. This applies to all efficacy, safety, and PK data.

Listings will include scheduled, unscheduled, retest and early discontinuation data.

Unscheduled measurements will not be included in by-visit summaries. Unscheduled measurements collected prior to the first dose of study medication will contribute to the derivation of the baseline value. Unscheduled measurements collected post baseline will contribute to the derivation of potentially clinically significant (PCS) post-baseline value and worst case value where required.

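### The unscheduled BARS taken when extrapyramidal symptoms need treatment enters no BARS table, so akathisia treated and resolved by Week 2 and Week 3 is tabulated as not worsened

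*SAP*

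**What the plan says.** **Objective and endpoint.** Protocol 5.2 sets the aim "To assess whether adjunctive administration of SEP-363856 is associated with extrapyramidal symptoms as measured by the Barnes Akathisia Rating Scale (BARS"; the sentence goes on to name AIMS and the Simpson-Angus scale. The matching endpoint in Protocol 6.2 is "Change from Baseline in BARS, AIMS and SAS scores at Week 2 and Week 3".

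**When the scales are rated.** Protocol Table 2 footnote t fixes the baseline rating: "BARS, AMES, SAS to be collected on Day -1 or Day 1 (predose". Protocol 11.9.2.6, 11.9.3 and 11.9.4 schedule the next ratings at Day 14 (+5 days), at follow-up 7 ± 2 days after the last dose, and at early termination. Footnote q adds: "Unscheduled BARS, AIMS, and SAS scales should be administered if a subject develops extrapyramidal symptoms (EPS) requiring treatment".

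**Treatment before Week 2.** Protocol 10.3.3 states "Treatment with propranolol (up to 120 mg/day) will be permitted as needed for akathisia" and also allows several agents for acute extrapyramidal symptoms.

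**Summaries.** SAP 16.7 says "BARS total score (observed value and change from baseline) will be summarized numerically by visit". It treats the four BARS items, and the worsened/unchanged/improved reading of the BARS global assessment, in the same by-visit way. SAP 7.3 says "Unscheduled measurements will not be included in by-visit summaries". For the Simpson-Angus scale, SAP 16.7 says "Shifts from baseline in SAS mean score classification will be summarized by visit and for the overall post-baseline period", and it counts early termination, follow-up and unscheduled visits after first dose in that period. The AIMS normal/abnormal classification has the same arrangement.

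**The concern.** Between the first dose and Week 2 no BARS is scheduled. If akathisia appears in that interval and is treated, the protocol's way of putting it on the scale is the unscheduled rating. By Week 2 the scheduled BARS may be a value on treatment, or a value after the episode has resolved.

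The SAP then has no BARS table in which the unscheduled rating can be counted. The omission is not neutral. The rating is triggered by symptoms bad enough to treat, so what is left out of the BARS tables is selectively the unfavourable information. At stake is whether someone who reads the BARS tables alone, on the scale dedicated to akathisia, gets a more reassuring picture than the data collected would give.

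**Working it through.** No figure in the plan is in dispute. The check compares the movement-disorder outputs in SAP 16.7 with the rule in SAP 7.3, and then works out the size.

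**1. Which outputs can contain an unscheduled rating**

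| Output in SAP 16.7 | By visit | Overall post-baseline, unscheduled included |
|---|---|---|
| BARS total (value and change) | yes | no |
| BARS four items | yes | no |
| BARS global: worsened/unchanged/improved | yes | no |
| AIMS total (value and change) | yes | no |
| AIMS total: normal/abnormal shift | yes | **yes** |
| AIMS global severity, incl. worsened/unchanged/improved | yes | no |
| Simpson-Angus mean (value and change) | yes | no |
| Simpson-Angus mean: normal/abnormal shift | yes | **yes** |

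BARS outputs that can contain an unscheduled rating: 0 of 3.

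**2. Does the exception in SAP 7.3 help?** SAP 7.3 lets unscheduled post-baseline values feed potentially clinically significant and worst-case derivations where these are required. SAP 16.7 specifies no such derivation for the BARS, so the exception has nothing to act on. Early-termination ratings are different: SAP 7.3 maps them to the next planned timepoint, so they do enter the by-visit tables.

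**3. One subject traced through.** Take a baseline global rating of 0, akathisia on Day 6 with a raised unscheduled BARS, treatment, and a global rating of 0 at Week 2 and Week 3. The subject is tabulated as unchanged at both visits. The Day 6 rating appears only in the listing.

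**4. Is the Simpson-Angus shift a back-up?** Footnote q triggers all three scales, the Simpson-Angus scale has an akathisia item, and its overall shift includes unscheduled visits. The score is the mean of 10 items and is abnormal above 0.3. SAP 16.7 says only that items are on a 5-point scale; assume 0 to 4. With the other nine items at 0:

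- akathisia item 1: 1/10 = 0.1, normal
- akathisia item 2: 2/10 = 0.2, normal
- akathisia item 3: 3/10 = 0.3, normal, since the cut-off must be exceeded
- akathisia item 4: 4/10 = 0.4, abnormal

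Isolated akathisia registers only at the top rating, so this back-up is weak.

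**5. Size (illustration).** Protocol 15.1 plans 22 subjects. Assume all are dosed and assessed, and let *k* have a raised unscheduled global rating that is back at baseline by both scheduled visits. The planned tables show 0/22 worsened from these subjects; a worst-value summary shows *k*/22:

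- *k* = 1: 1/22 = 4.5%
- *k* = 2: 2/22 = 9.1%
- *k* = 3: 3/22 = 13.6%

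The documents give no risk *p* of such an episode. With independent subjects, the chance of at least one among 22 is 1 − (1 − *p*)^22. For assumed *p* of 2%, 5%, 10% and 15% this is 36%, 68%, 90% and 97%.

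**The case against.** **The endpoint is delivered as written.** It is change from baseline at Week 2 and Week 3, and by-visit summaries give exactly that. This stands: a worst-value row is an addition, not the repair of a broken endpoint, and the subjects concerned remain in the tables with their scheduled values. But AIMS and Simpson-Angus share the same endpoint, and the SAP still gave each an overall post-baseline output.

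**The asymmetry may be a convention.** The overall period is attached only to normal/abnormal classifications. The BARS has none, and its global item is handled just as AIMS global severity is. This also stands, and it argues against calling the gap a BARS-specific oversight. The effect on the tables is the same, and it extends the point to AIMS global severity.

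**The episode is recorded elsewhere.** A reader might infer that treated akathisia is captured only on the unscheduled BARS, or that the extrapyramidal objective as a whole can come out falsely negative. The documents do not support either reading. Subjects are in-clinic, and adverse events are collected on each day from Day 2 to Day 13 (Protocol 11.9.2.4 and 11.9.2.5). Akathisia reported as an event is counted by preferred term, severity, relationship and dose at onset (SAP 16.1). Its treatment enters the medication table (SAP 12), and every rating on the three scales is listed (SAP 16.7). Akathisia still present at Week 2, or rated at early termination, is summarised.

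These sources do not fully replace a BARS summary. Adverse events are elicited without specific prompting (Protocol 11.6.1), and no grouping of extrapyramidal terms is among the planned tables. The medication table counts by drug class and preferred name, not by indication or new start, and beta-blockers are also allowed for hypertension (Protocol 10.3.3).

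**Nothing causal follows.** The study is single-arm, on a background antipsychotic, and the BARS is purely descriptive. A worst-value row would show how often ratings worsened on treatment, not that the drug caused it.

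**Conclusion.** The point holds for the BARS tables. As written, no unscheduled post-baseline BARS contributes to any BARS summary, and the omission runs in one direction. The AIMS global severity summary has the same limit. The gap is in the BARS component of the extrapyramidal objective, not the whole objective, because the adverse event tables, the medication table and the listing should still show the episode.

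The displayed incidence of BARS worsening falls by 4.5 percentage points per affected subject. That rests on all 22 planned subjects being dosed and assessed, and on each case having a raised unscheduled global rating that returns to baseline by both Week 2 and Week 3. How many such cases to expect cannot be derived from the documents. The judgement that the Simpson-Angus shift is a weak back-up rests on 0–4 item coding and on akathisia without other Simpson-Angus signs.

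This is a modest gap in a descriptive safety output, worth closing because closing it is nearly free.

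**What to change.** In SAP 16.7, add an overall post-baseline summary based on the worst (highest) value for:

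- the BARS global clinical assessment, classified as worsened, unchanged or improved against baseline;
- the BARS total score, value and change from baseline;
- the AIMS global severity score, classified in the same way.

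State that early termination, follow-up and unscheduled visits after first dose count towards this period, reusing the sentence that SAP 16.7 already applies to the AIMS and Simpson-Angus classification shifts. This gives the worst-case exception in SAP 7.3 something to act on, so SAP 7.3 itself needs no change. State the denominator: safety-population subjects with a baseline and at least one post-baseline rating.

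Optionally, report the number of subjects who start an anti-extrapyramidal or anti-akathisia medication after first dose, so that Week 2 ratings can be read with that in mind.

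Cost: a few sentences of SAP text and a few table rows. All the data are already collected, and study conduct does not change.
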